We will conduct a hybrid type III effectiveness-implementation trial with a longitudinal cluster randomized design to answer questions related to implementation strategy and program effectiveness. We will also apply mixed methods to investigate implementation strategy mechanisms. During the active implementation period, all 30 clinics in the two participating health systems will receive *SAFE Firearm* materials, including brief training in program delivery, cable locks, and the deployment of an EHR implementation strategy. Half of the clinics will be randomized to only receive the EHR implementation strategy (*Nudge*); the other half will be randomized to receive *Nudge* plus 1 year of facilitation to target additional clinician and organizational implementation barriers (*Nudge+*). We will

collect the primary implementation outcome for 1 year following the active trial year to allow for comparisons between the active and sustainment periods. Results will guide future efforts to promote firearm safety as a universal suicide prevention strategy.

EQUITY SUPPLEMENT PURPOSE:

Prior to launching the full trial, we are piloting the delivery of the *SAFE Firearm* program in 2 clinics in each health system during an approximately 4-5 month period. Pilot procedures will mirror the procedures described in the protocol and use the same parent survey instrument (more details are below). After the pilot, we will conduct this sub-study. Specifically, we will explore any signals of disparities and examine *SAFE Firearm* delivery by children's medical complexity (per ICD-9 and -10 codes) and race/ethnicity. Because we anticipate that clinicians will provide helpful contextualization for the program that will be informative for facilitation for the program and for the broader literature on firearm safety counseling, regardless of whether we detect differences in program delivery, we will interview KPCO and HFH clinicians who participated in the pilot to identify specific delivery barriers, and convene key stakeholders (e.g., facilitation leaders, pediatric leadership) for virtual meetings. We expect that this step will prime facilitation for trial launch. The goal of this sub-study is to learn more about barriers to delivering the *SAFE Firearm* program equitably to all patients, regardless of medical complexity and race/ethnicity, and to optimize facilitation to address disparities.

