- **Aim 1 Analysis.** Our power analyses are based upon the primary implementation outcome of reach, consistent with best practices for hybrid type III trials.⁶¹ All other implementation outcomes are secondary. Our sample sizes for the project are determined by the fixed number of parent-youth dyads, PCPs, and pediatric clinics within our two health systems. Data are clustered within health system, clinic, and PCP. We expect that approximately 48,475 parents of youth will be eligible to participate each year, and expect to include data from 151 PCPs, within 41 clinics. Therefore, we anticipate obtaining EHR reach data for 48,475 patients during the one-year active implementation period. We base our power calculations on our study design and prior research from our group demonstrating that current PCP use of the *SAFE Firearm* program components are 28% for brief counseling on safe firearm storage and 2% for offering cable locks.¹⁴ We used the PASS power calculation program,⁶² assuming an estimate of an ICC of .07 for explained variance among both PCPs and clinics,⁶³ and conclude that we will have 80% power to detect small effects of the less intensive implementation condition (*Nudge*) on reach (Cohen's d = 0.25 and 0.29, respectively).⁶⁴ Alpha is set at .05 (two-tailed). A small to moderate effect is reasonable to expect based on prior research demonstrating that EHR nudges using active choice approaches produce effects in this range.⁵¹ Because the clinics will be our unit of randomization, it was not necessary to account for the health system ICC in the power analysis. We will account for any differences between health systems by weighting health system the strongest in our covariate constrained randomization. Also, we will conduct a sensitivity analysis that controls for health system as a fixed effect in our analyses and will explore whether intervention effectiveness varies significantly by health system. Our approach is consistent with similar work that has been published in leading medical journals (i.e., Navathe et al., 2019, *JAMA*, Sharma et al., 2019, *JAMA Oncology*). In Aim 1, the primary dependent variable is reach. For each observation period (active implementation, sustainment) and for each implementation condition (*Nudge*, *Nudge+*), we will describe the proportion of clinicians who reported having delivered the program with EHR reach. We will calculate EHR reach using three binary outcomes: received counseling (yes/no), offered lock (yes/no), both (yes/no). We will then conduct separate models. In the first set of models, we will examine whether the odds of receiving components of *SAFE Firearm* increased more in the *Nudge+* group compared with the *Nudge* group between the active implementation and sustainment periods. The fixed effects in the model will include implementation condition (*Nudge*, *Nudge+*), time (active implementation, sustainment), and their interaction; the magnitude and statistical significance of the parameter estimate for the interaction term will be of primary interest. Given the nested data (i.e., parent-youth dyads nested within PCPs; PCPs nested within clinics; clinics nested within health systems), analyses will rely on 3-level logistic mixed effects regression models for reach as a dichotomous implementation outcome.^{65,66} Linear mixed effects regression will be used to model continuous secondary outcomes (e.g., acceptability). For all models, our independent variable of interest will be a binary

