Statistical Analysis Plan (SAP)
Adolescent and child Suicide Prevention In Routine clinical Encounters (ASPIRE) study

Official Title: A comparative effectiveness trial of strategies to implement firearm safety promotion as a universal suicide prevention strategy in pediatric primary care

Funding Agency: National Institute of Mental Health (NIMH)

NIH Grant Number: R01 MH123491

University of Pennsylvania Protocol Number: 844327

Principal Investigator: [name]

ClinicalTrials.gov Number: NCT04844021

Original SAP: 09 August 2021

Final SAP: 03 July 2023

Table of Contents

Final Statistical Analysis Plan	2
SAP amendments	4
Original Statistical Analysis Plan	6
Study blinding details	7

Final Statistical Analysis Plan

Date of approval by study team: 03 July 2023 (Prior to unblinding and data analyses; primary outcome data analyses commenced on 25 July 2023)

ASPIRE Statistical Analysis Plan for Primary Comparison of Nudge vs Nudge+

Primary outcome: Reach, defined as the composite (multiplicative) of two binary outcomes:

- 1) discussion of safe firearm storage (Yes/No)
- 2) offered a cable lock (Yes/No)

Therefore, the primary outcome will be coded as a 1 (successful program delivery) if both components were documented as “Yes” in the EHR; otherwise, the primary outcome will take value 0. The primary outcome is measured at the patient-visit level. If the same patient has multiple visits data from each visit will be included in the analysis. If multiple children in the same family, all visits for all children will be included.

As a secondary analysis, we will analyze 1) and 2) individually. We hypothesize that the analysis of component 2 (cable lock offers) will provide results similar to the results for the composite Reach outcome since fewer clinicians will endorse the cable lock than discussion and it is rare for clinicians to offer the lock without also doing the discussion.

Missingness in the primary outcome: Due to the nature of the EHR systems at the two sites, there is a non-negligible amount of missingness in the two binary outcomes that make up the composite Reach variable. More specifically, there is a large amount of missingness in the “offered a cable lock” outcome at one site, since clinicians were able to exit the EHR smartlist after documenting the first outcome about safe storage discussion.

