Unfortunately, missingness in one of the two outcomes induces missingness in the composite Reach outcome. In the primary analysis, we will treat any missing value as a “No.” As a result, there will be no missing values in the Reach outcome for the primary analysis.

Statistical analysis plan:

Here, we describe the statistical analysis plan for the primary analysis of Reach.

Check balance across arms:

We will first calculate standardized mean differences (SMD) of both individual-level (sex, race, etc.) and clinic-level (size, presence of stakeholder, etc.) variables. Variables with a SMD greater than 0.2 will be included as covariates in the outcome models. The SMD for a given variable will be calculated as:

$$SMD = \frac{\bar{Y}_2 - \bar{Y}_1}{\hat{\sigma}_{Pooled}}$$

where \bar{Y}_2 is the sample average of Nudge+ cluster means; \bar{Y}_1 is the sample average of Nudge cluster means; and $\hat{\sigma}_{Pooled}$ is the standard deviation of all N=30 cluster means.

Primary outcome model:

Missing values in the Reach outcome will be imputed as having not delivered the S.A.F.E. Firearm program. Given the definition of Reach will be completely observed (no missingness), we plan to model the patient-level binary Reach outcome using a logistic generalized estimating equation (GEE) with an exchangeable correlation at the clinic level. This model provides an estimate of the marginal effect of Nudge+ versus Nudge, i.e., the expected difference in the population if all clinics had received Nudge+ compared to giving all clinics Nudge only. In addition to the clinic-level indicator of randomized treatment assignment (corresponding to the parameter of interest), we will include the following set of covariates: sex (patient-level), health system (clinic-level), clinic size measured by number of well-child visits in the year prior to the trial launch (clinic-level), and clinician partner status (clinic-

level). We chose to include patient-level sex based on pilot findings that the rate of program delivery differs significantly for male versus female patients and by patient race. The three clinic-level covariates will be included because they were used in the covariate constrained randomization and are therefore anticipated to be highly related to Reach.

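### The protocol's 80% power figure (effect of Nudge, 41 clinics, no margin) does not describe the SAP's primary test, and neither document gives power for that test

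*Protocol*

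**What the plan says.** Protocol, Statistical Analysis, Aim 1 Analysis. This is the only current power statement for Aim 1. The investigators "expect to include data from 151 PCPs, within 41 clinics", anticipate reach data on 48,475 patients in the active year, take an ICC of .07 for clinicians and clinics, and use two-tailed alpha .05. The starting rates are "28% for brief counseling on safe firearm storage and 2% for offering cable locks". They conclude that "we will have 80% power to detect small effects of the less intensive implementation condition", with d = 0.25 and 0.29. No margin is mentioned. The same section names the condition-by-time interaction, active implementation against sustainment, as the estimate of main interest.

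Protocol, Introduction and Purpose: "all 30 clinics in the two participating health systems will receive" the programme materials and the EHR strategy. Half of the clinics also receive facilitation.

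SAP, Final Statistical Analysis Plan. The title line reads "ASPIRE Statistical Analysis Plan for Primary Comparison of Nudge vs Nudge", the second arm being Nudge+. The primary outcome is the composite of discussion and lock offer. The model contains arm and covariates but no time term. The cluster count is 30: the pooled quantity in the balance check "is the standard deviation of all N=30 cluster means". Under Hypothesis testing, Type I error is .05 and the margin is 10 percentage points. Equivalence needs the whole confidence interval inside the margin. Superiority needs the lower limit above the margin's upper bound. No power or detectable difference is given.

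**The concern.** The trial asks whether Nudge is enough or facilitation is needed. The SAP rule can end in equivalence, superiority or neither, and a reader needs to know how likely each ending is. The only figure on offer is an 80% that belongs to something else:

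- **Contrast.** It concerns the effect of Nudge. Both arms receive Nudge, so that effect is not a randomised contrast in this trial.
- **Outcome.** The starting rates are for the two components. None is given for the composite.
- **Clusters.** It assumes 41 clinics; the trial has 30.
- **Rule.** It has no margin. The SAP requires a gain shown to exceed 10 points.
- **Test.** The protocol's own test of main interest, the interaction, is different again from the SAP's comparison of arms.

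If the 80% is left to stand for the primary test, an inconclusive result could be read as coming from a trial with 80% power to decide the question.

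**Working it through.** **Inputs.** From the protocol's Aim 1 Analysis: 151 clinicians, 48,475 patients, ICC .07, alpha .05 two-sided, d = 0.25 and 0.29, 41 clinics. From the protocol's Introduction and the SAP: 30 clinics. From the SAP: the 10-point margin and, from the pilot table under SAP amendments, 45.3% for both components in the EHR.

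Assumptions: clinician and patient numbers still apply at 30 clinics; clinic sizes are equal; the confidence interval is 95%; degrees of freedom are clinics minus 5 (intercept, arm, three clinic covariates). Nudge reach is taken as 45.3%, 28%, 20% or 10%, the low values because missing documentation counts as No. Residual ICC (clinic + clinician) runs from .07+.07 to .01+.01, the low end allowing for covariate adjustment.

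**Formula.** Per-arm variance in SD² units, with k clinics:

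V = ρc/(k/2) + ρp/(151/2) + (1 − ρc − ρp)/(48,475/2)

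SE(d) = √(2V); SE(risk difference) = √(V·[p0(1−p0) + p1(1−p1)]). Power comes from the noncentral t.

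**1. The protocol's figure, 41 clinics, ICC .07 at both levels.** V = .003415 + .000927 + .000035 = .004377, so SE(d) = .0936. Power is 74% at d = 0.25 and 85% at d = 0.29; 80% power falls at d = .269. With ICC .07 at clinic level only, 80% falls at d = .239. The stated 0.25 lies between these two readings. The software settings and the ICC split are not given, so no error in that run follows.

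**2. Same test, 30 clinics, ICC .07 at both levels.** V = .004667 + .000927 + .000035 = .005629, so SE(d) = .1061. Power is 62% at d = 0.25 and 75% at d = 0.29; 80% needs d = .309. At .035+.035, power at d = 0.25 falls from 96% to 89%.

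**3. SAP superiority rule, 30 clinics, Nudge reach 45.3%, true gain 15 points.** The sum of p(1−p) is .2478 + .2394 = .4872.

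- .07+.07: SE = √(.005629 × .4872) = 5.24 points; noncentrality (15 − 10)/5.24 = 0.95. Superiority 15%, equivalence near 0, no verdict 85%.
- .01+.01: V = .000667 + .000132 + .000040 = .000840; SE = 2.02 points; noncentrality 2.47. Superiority 66%, no verdict 34%.

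The true gain needed for 80% superiority power is 24.8 points at .07+.07 (SE there 5.07; 14.8/5.07 = 2.9) and 15.9 points at .01+.01 (SE 2.02; 5.9/2.02 = 2.9).

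**4. SAP equivalence rule, true difference zero** (simulation, 1,000,000 draws, with the estimated SE allowed to vary). At .07+.07 and 45.3% reach the SE is 5.28 points and the typical half-width 2.06 × 5.28 = 10.9, wider than the margin. At 10% reach the SE is 3.18 and the half-width 6.6. Probability of declaring equivalence:

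| ICC (clinic + clinician) | reach 45.3% | 28% | 20% | 10% |
|---|---|---|---|---|
| .07+.07 | 4% | 12% | 26% | 71% |
| .035+.035 | 46% | 62% | 78% | 98% |
| .01+.01 | 99% or more | 99% or more | 99% or more | 99% or more |

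**The case against.** Sample size here is set by the clinics and patients available, so the power statement chose nothing. The margin and decision rule were fixed before unblinding, and an inconclusive result will show in the reported interval. The results also turn on ICC values that are partly assumed. The 45.3% is a pre-launch pilot rate, not an estimate for the Nudge arm, and it is the least favourable reach tried for equivalence. All of this stands. It limits the remedy to restating a figure and rules out any single replacement number, but it does not make the 80% apply to the SAP's test.

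Three stronger readings are tempting and not supported.

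- **The software run is wrong.** Its settings are not stated, and d = 0.25 falls between two reasonable readings of the ICC.
- **Superiority power stays well below 80% in every setting at d = 0.25 or 0.29.** The protocol does not offer those values as Nudge+ minus Nudge effects. Read in order, 0.29 belongs to lock offers at 2%, where it is 0.29 × √(.02 × .98) = 4.1 points. Moved to reach of 28–45.3%, with ICC .01+.01 and a 90% interval, superiority power reaches 69%.
- **The trial cannot answer its question.** With a small residual ICC, equivalence at zero difference is nearly certain to be declared.

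The SAP refers its original version to a published protocol paper, which is not supplied. The gap can be asserted only for these two documents.

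**Conclusion.** The mismatch is plain in the text and needs no modelling. The protocol's 80% concerns another contrast, 11 more clinics and a test without a margin, and neither document gives power for the SAP rule. The figure should be corrected and should not be quoted as the power of the primary test.

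The size depends on assumptions. The fall from about 74% to 62% at d = 0.25 holds for ICC .07 at both levels with 151 clinicians and 48,475 patients retained. At reach of 45.3%, the gain needed for 80% superiority power runs from about 25 points (.07+.07) to 16 points (.01+.01), and no verdict at a true 15 points from about 85% to 34%. Equivalence at zero difference runs from 4% to over 99% across the ICC and reach values tried. That spread is itself the reason to state the residual ICC and reach. It does not show that the trial is too small.

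**What to change.** Correct the Aim 1 Analysis to 30 clinics and stop presenting its 80% as the power of the primary comparison. Add a dated statement of the probabilities of equivalence, superiority and no verdict under the SAP rule at 30 clinics. It should cover stated ranges of Nudge reach (10–45%), true difference, and residual ICC (.01+.01 to .07+.07). The SAP records that "primary outcome data analyses commenced on 25 July 2023". If written after that date, both the correction and the new statement should be labelled post hoc, so that neither passes for advance planning.

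The cost is one recalculation and one paragraph. No clinics, data or decision rule change. The downside is a less favourable stated power over much of the range.

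Writing out the interval level, the inferiority rule and the wording for an inconclusive result would be minor clarifications, separate from this point.

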Primary outcome variables:

- Aim 1. Clinician-reported reach (program delivery as documented in the EHR)
- Aim 2. Staff-reported clinic adaptive reserve
- Aim 3. Parent-reported firearm storage behavior

Secondary/Other outcome variables (Moderators and mediators to be measured):

- Aim 1. Parent-reported clinician fidelity, cable lock distribution, acceptability, cost
- Aim 2.
 - Moderators: Clinician burnout, clinician attitudes towards firearms counseling
 - Mediators: Clinician motivation
- Aim 3. Youth suicide attempts, deaths, and unintentional firearm injury and mortality

BACKGROUND:

Youth suicide deaths are on the rise in the United States (U.S.). Firearms are a common and lethal method of suicide attempt. Reducing access to lethal means is a promising yet underused suicide prevention strategy.²⁷ Firearms are a critical target of such efforts^{28,29} given that they are present in one in three U.S. homes and these numbers are increasing in the wake of Covid-19.³⁰ Recent research has found that only 3 in 10 firearm-owning families with children store all guns in their home in the safest manner: locked and unloaded. Approximately 4.6 million U.S. children (7%) live in homes in which at least one firearm is stored unlocked and loaded.³¹ Given that the presence of firearms in the home is a robust risk factor for suicide,³² safe storage of firearms in the home is imperative for reducing youth suicide attempts and death. Simulation research has found that even a modest increase in safe firearm storage could prevent as many as 32% of youth firearm deaths due to suicide and accidents.¹⁶ Thus, efforts to increase implementation of interventions to improve safe storage could save young lives nationally.

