Equity Supplement Procedures: The Penn interview team will work with the ASPIRE Site PIs at Henry Ford Heath System and Kaiser Permanente Colorado to identify potential participants who engaged in piloting procedures. The site PIs and/or Penn team will reach out via email with an invitation to participate. If clinicians are interested in participating, the interview team will schedule a date and time that is convenient to conduct a qualitative interview by phone or videoconferencing if the participant prefers. During the call but before the interview begins, the interview team will obtain consent (see Informed Consent section below for more details). The interview will not take place if the participant does not provide informed consent. The interview will be audio-recorded. Based on what is allowed at each health system, participants will receive a \$50 electronic gift card (or if no gift card is permitted for research study incentives by the health system, we will send a personalized thank you email). After analyzing the interviews, we will use existing, ongoing meetings with clinical stakeholders to gather feedback on our findings. We will present our findings, which will allow stakeholders to select specific strategies (e.g., collaborative problem-solving) within facilitation to target disparities in *SAFE Firearm* delivery. We expect that this step will prime facilitation for trial launch and increase the likelihood of equitable outcomes.

2. Data Collection:

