
indicator of implementation condition assigned at the clinic level. All analyses will be conducted using MPlus to appropriately estimate multilevel regression models.⁶⁷ Although we expect our groups to be balanced with respect to patient and PCP characteristics, we will consider including the following variables, extracted from the VDW, as relevant covariates: health system (HFH, KPCO); youth demographics (age, gender, race and ethnicity, patient language); PCP demographics (specialty/degree, gender, year graduated from medical school); and public census data (socioeconomic indicators for patients based on geocoded patient addresses). In sensitivity analyses, we will examine each set of models separately by health system to account for structural differences in how care is delivered within the two systems. Sex and race/ethnicity, drawn from the EHR and survey, will be added to all models as fixed effects to account for the potential role they may play in implementation strategy and intervention effectiveness. We will also investigate whether sex moderates the effects of the implementation strategies. Given the potential high non-response to the parent survey following the visit, we will use inverse probability weighting to adjust for parental survey non-response (Skinner, 2011). Specifically, inverse probability weighting allows us to use patient, clinician, and clinic information from the EHR about both respondents and non-respondents to assign larger weights to survey responses from participants who are under-represented in the sample. For example, if we find that parents who are ethnic and/or racial minorities have a lower response rate than parents who are not ethnic and/or racial minorities, inverse probability weighting would give more weight in the analysis to survey responses from parents who are ethnic/racial minorities.

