- **Aim 2 Analysis.** *Quantitative analysis.* For our 2-2-1 mediation analyses, we will have approximately 76 PCPs and 20 clinics per study arm. Using the PASS power calculation program,⁶² we anticipate these sample sizes will yield sufficient power to detect a moderate indirect effect (Cohen's $d = .44$) through the clinic-level mediator (i.e., clinic adaptive reserve). We assume there will be a large effect of the strategy on the mediator and of the mediator on the outcome based on previous research.⁶⁸ This is a conservative estimate because the calculation does not account for the additional power that will be gained due to the two measurement time-points for each PCP. We will conduct exploratory analyses to investigate motivation as a mediator. Mediation will be tested using the product of coefficients approach for multilevel mediation analysis,⁶⁹⁻⁷¹ which we have used in previous studies.⁷² In this approach, the total effect of the implementation strategy is parsed into direct and indirect effects associated with the mediator. We will test each mechanism in a separate 2-2-1 mediation model. Path "a" represents the effect of the implementation strategy (*Nudge, Nudge+*) at the clinic level on the clinic-level mediator (i.e., clinic adaptive reserve). Path "b" represents the relationship between the clinic-level mediator (i.e., adaptive reserve) and the three binary reach outcomes (counseling, cable lock, both). We will calculate change in reach for each of the two time-points using the 6 month period preceding each survey administration. An unbiased estimate of the mediated effect is derived via the product of the "a" and "b" paths (i.e., $a \times b$) from these analyses.^{70,71,73} We will test the statistical significance of the mediated effects using the joint significance test.⁷⁴ We will use Monte Carlo simulation methods to derive confidence intervals.⁷⁴⁻⁷⁷ We will repeat this model for our exploratory mediator, motivation. Moderators of the strategies' effects will be tested separately by adding terms for each moderator and its interaction with the implementation strategy to the Aim 1 models only during the active implementation period. These models will estimate the conditional relationships between the implementation strategies and implementation outcomes across different values of the putative moderators. *Qualitative analysis and mixed methods.* Text answers from open-ended questions with parents from Aim 1, and digitally recorded and transcribed interviews with PCPs, point people, and leaders on the mechanisms of the implementation strategies, will be loaded into NVivo qualitative data analysis software. Analysis will be led by the research team guided by an integrated approach,⁷⁸ which outlines a rigorous, systematic method for analyzing qualitative data using an inductive and deductive process of iterative coding to identify recurrent themes, categories, and relationships. We will ensure at least 80% interrater reliability amongst our coders (we will have at least two). The structure of our mixed methods approach is sequential (quantitative data is collected before qualitative data and quantitative data is weighed more strongly than qualitative; QUAN>qual). The function is of complementarity (to elaborate upon the quantitative findings to understand the *how* of implementation), and the process is connecting (having the qualitative data set build upon the quantitative data set).⁷⁹ To integrate the quantitative and qualitative results, we will follow guidelines for best practices in mixed methods⁸⁰ as well as our previous experiences with mixed methods implementation research.⁸¹⁻⁸⁴

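### No planned analysis compares the racial/ethnic gap in delivery between Nudge+ and Nudge, and the Protocol and SAP disagree on whether race/ethnicity is in the reach model at all

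*Protocol*

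**What the plan says.** **Protocol, Statistical Analysis, Aim 1 (final approved version).** Sex and race/ethnicity, taken from the EHR and the survey, are to be "added to all models as fixed effects to account for the potential role they may play in implementation strategy and intervention effectiveness". The next sentence is "We will also investigate whether sex moderates the effects of the implementation strategies". Race/ethnicity has no matching sentence. The same section explores variation in effect by health system.

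**Protocol, outcome list and Aim 2 analysis.** The listed moderators are clinician-level: "Moderators: Clinician burnout, clinician attitudes towards firearms counseling". The method for testing a moderator is given as "adding terms for each moderator and its interaction with the implementation strategy to the Aim 1 models only during the active implementation period". It is not applied to race/ethnicity.

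**Protocol, equity supplement.** The supplement examines delivery by race/ethnicity in four pilot clinics, and later repeats that analysis descriptively in the same four. A 10% difference in delivery between patient groups is the level treated as clinically significant. The findings feed into facilitation so that it can target disparities: "We expect that this step will prime facilitation for trial launch and increase the likelihood of equitable outcomes". Facilitation is the component that separates Nudge+ from Nudge.

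**SAP, Primary outcome model.** Sex is included because the pilot found that "the rate of program delivery differs significantly for male versus female patients and by patient race". The covariates then listed are sex, health system, clinic size and clinician partner status. Under the SAP's balance check, any other variable, race included, enters only if its SMD between arms exceeds 0.2, and then as a covariate.

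**The concern.** A role in how well a strategy works is effect modification. A main effect for race/ethnicity lets the delivery rate differ between groups but imposes one arm odds ratio on all of them. The SAP's listed covariates may leave race out altogether, which conflicts with the Protocol's commitment to put it in every model and with the pilot finding that the SAP itself cites.

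This is more than a generic request for another subgroup. The documents report a pilot difference by race, describe work to point facilitation at disparities, give facilitation to one arm only, and state an expectation of more equitable outcomes. Without an arm contrast in the gap, a conclusion of equivalence could coexist with facilitation that closes a material gap, and a conclusion of superiority with facilitation that widens one. The reports would not show which had happened.

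**Working it through.** **1. Search for a planned contrast.**

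| Place | What is planned for race/ethnicity | Compared by arm? |
|---|---|---|
| Protocol, Aim 1 | Fixed effect in all models | No; moderation for sex only |
| Protocol, Aim 2 moderators | Not listed | No |
| Protocol, equity supplement | Weighted GEE in pilot clinics, later repeat | No arm comparison described; 4 clinics |
| SAP, balance check | Covariate if SMD > 0.2 | No |
| SAP, primary model | Not in the covariate list | No |

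**2. Can a common-effect model separate narrowing from widening?** Illustrative set-up: equal arms, overall reach of 45% in Nudge and 55% in Nudge+, smaller group 50% of visits, logistic models fitted to expected counts without clustering.

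- Scenario A, Nudge+ closes a gap: Nudge 50% vs 40%, Nudge+ 55% vs 55%.
- Scenario B, Nudge+ opens a gap: Nudge 45% vs 45%, Nudge+ 60% vs 50%.

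The main-effects fit gives the same coefficients in A and B: arm 0.402, race -0.202. With smaller-group shares of 20% and 35% the coefficients are again the same in A and B. A model without race sees only 45% vs 55% in both scenarios.

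The interaction odds ratio separates them:

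- A: Nudge group OR = (0.40/0.60)/(0.50/0.50) = 0.667; Nudge+ group OR = 1; ratio 1/0.667 = 1.50.
- B: Nudge group OR = 1; Nudge+ group OR = (0.50/0.50)/(0.60/0.40) = 0.667; ratio 0.667.

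**3. Precision of the missing contrast.** The documents give no power figure for it. Their only Aim 1 figure, 80% power at d = 0.25 and 0.29, concerns overall reach and does not bear on this point.

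Inputs from the documents: 48,475 patients in the active year (Protocol, Aim 1); 30 clinics (SAP), taken here as 15 per arm; pilot EHR reach for both components 45.3% (SAP amendments), rounded to p = 0.45. Each patient is counted as one visit, so visits per clinic are 48,475/30 = about 1,616.

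Assumptions not in the documents: smaller group 30% of visits, the same in every clinic; equal clinic sizes; between-clinic SD of the gap, τ, varied.

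- Variance of one clinic's gap = p(1-p)(1/n1 + 1/n2) + τ². With n1 = 485 and n2 = 1,131, the first part is 0.2475 × 0.002946 = 0.00073.
- SE of the arm difference in gaps = √(2/15 × variance).
- 95% half-width = 2.048 × SE. Difference detectable with 80% power = (2.048 + 0.855) × SE, with t on 28 df.

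| τ (points) | SE | 95% half-width | Detectable with 80% power |
|---|---|---|---|
| 3 | 1.5 | 3.0 | 4.3 |
| 5 | 2.1 | 4.3 | 6.0 |
| 8 | 3.1 | 6.3 | 9.0 |
| 9 | 3.4 | 7.0 | 10.0 |
| 10 | 3.8 | 7.7 | 11.0 |

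At τ = 5: variance = 0.00073 + 0.0025 = 0.00323; SE = √(0.1333 × 0.00323) = 0.0208; detectable difference = 2.903 × 0.0208 = 0.060.

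The Protocol ties 48,475 to 41 clinics. Using 48,475/41 = about 1,182 visits in each of 30 clinics moves the τ = 5 result only from 6.0 to 6.3 points. Between-clinic variation in the gap dominates, not the number of visits.

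**The case against.** - **The Protocol's wording may mean ordinary adjustment.** This stands in part. Accounting for a role is language that statisticians also use for covariate adjustment, and the Aim 1 section counts the condition-by-time interaction among its fixed effects. But that interaction is named, as is moderation by sex; none is named for race/ethnicity. A reader might infer that the method plainly fails its stated purpose. The text does not support so firm a reading. The missing arm comparison remains on either reading.
- **A racial gap by arm is not a stated aim, outcome or moderator.** True. The equity supplement is a sub-study about barriers to delivery, the six-stage description of facilitation names no disparity component, and the explicit disparity feedback goes to the pilot clinics. This limits the request to an exploratory analysis. It does not remove the stated link from the equity findings to facilitation.
- **Precision may be poor.** This stands. A reader might infer that the contrast would be estimated more finely than the 10% threshold. That fails at a between-clinic gap SD of about 9 points, and small or unevenly distributed groups would make it worse. Also, the 10% applies to a gap between patient groups; the documents set no threshold for an arm difference in gaps.

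**Conclusion.** The point holds as a gap in the planned analyses and a mismatch between the two documents. The Protocol puts race/ethnicity in every model; the SAP's primary model omits it unless an imbalance rule is triggered, while citing a pilot difference by race. Neither plans an arm comparison of the racial/ethnic gap.

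A reader might go further and infer that the trial cannot answer the question. The documents do not support that: race/ethnicity is among the EHR elements available for extraction, so one additional model could address it. Nor do they say that equity by arm will be claimed or denied; they state an expectation. It would also be inexact to say that race enters only as a main effect, since under the SAP it may not enter at all.

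How informative the added contrast would be is uncertain. With a 30% smaller group, the detectable difference in gaps is about 6 points at a between-clinic SD of 5 and about 10 to 11 points at an SD of 9 to 10. Both the share and the SD are assumptions. The primary comparison of Nudge+ with Nudge is not put in doubt.

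**What to change.** 1. Reconcile the Protocol's Aim 1 text with the SAP by including EHR race/ethnicity in the SAP reach model, with unknown as its own category.
2. Add one exploratory model of active-year reach with an arm-by-race/ethnicity term alongside arm-by-sex. Report the Nudge+ minus Nudge risk difference within each group, the gap within each arm, and the arm difference in the gap, with clinic-robust, small-sample-corrected intervals.
3. Read the 10% threshold only against the gap within each arm. Interpret the arm difference in gaps by its interval.

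The cost is a short addition to the plan and one more model on EHR data that the Protocol already commits to using. The downside is one additional exploratory contrast, to be labelled as such. The primary test and alpha do not change.
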